## **6 Research Intervention**

### **6.1 Intervention**

The intervention was administered as follows: (1) The control group received Idebenone (Shenzhen Neptunus Pharmaceutical Co., Ltd., National standard: H10970362, Specification: 30mg) orally, at a dose of 30mg per time, three times a day, after meals for 12 consecutive weeks. (2) The treatment group received Naohuan Dan combined with Idebenone. The main components of traditional Chinese medicine

were Codonopsis Radix 20g (Batch number: 1031653), Radix Rehmanniae Preparata 25g (Batch number: 1050973), Drynariae Rhizoma 15g (Batch number: 0117293), Acori Tatarinowii Rhizoma 10g (Batch number: 1021283), Radix Polygaiiae 8g (Batch number: 9086013), Poria Cocos 12g (Batch number: 1051133), etc. The traditional Chinese medicine granules were provided by Guangdong Yifang Pharmaceutical Co., Ltd., at a dose of one per day, delivered with warm water in the morning and evening, and taken orally for 12 consecutive weeks. (3) Basic and symptomatic treatments were given to both groups according to the patient's underlying diseases and complications, such as antihypertensive and hypoglycemic treatments.

## **6.2 Study Intervention Adherence**

Patients who are able to take medication on time and in the correct dosage, attend regular hospital follow-ups, do not take prohibited drugs, and cooperate with medical evaluations during the course of treatment are considered to have good compliance.

Methods to improve compliance include: (1) providing medication records and instructing patients to record medication intake daily, which can be returned during the next follow-up visit; (2) providing detailed explanations and addressing patient questions during the first medication distribution, while affirming the patient's contribution to research; (3) issuing medication in short-term doses and reminding patients of their next follow-up appointment in advance.

# **7 Study Intervention Discontinuation/Subject Discontinuation and Withdrawal**

## **7.1 Study Intervention Discontinuation**

The enrolled patients may discontinue treatment at any time for any reason or, in case of any adverse event, at the discretion of the investigator. Furthermore, the investigator may stop the treatment of a patient if the patient is deemed unsuitable for treatment, violates the study protocol, or for management and/or safety reasons.

The subject must discontinue treatment but may continue to be monitored in the

study if any of the following occur: 1) the patient or the patient's family requests discontinuation of treatment; 2) an intercurrent illness which interferes with further treatment occurs; 3) the investigator determines that the patient should be withdrawn from the study; 4) poor compliance by the patient; 5) the investigator believes that continuing to administer the investigational drug to the subject would place the subject at unnecessary risk based on the subject's medical condition or personal situation; 6) completion of the treatment as outlined in the protocol.

## **7.2 Subject discontinuation/withdrawal from the study**

If a patient or their family withdraws their informed consent to participate in the study, the enrolled patient must be withdrawn from the study. If a patient withdraws from the study, they will no longer receive treatment or participate in planned visits. If a patient is lost to follow-up, they must also be withdrawn from the study.

## **7.3 Lost to follow-up**

Timely education and reminders should be provided to enrolled patients. The next follow-up appointment should be scheduled during each visit, and the patient's contact information should be recorded to facilitate timely communication, enhance medication adherence and patient follow-up compliance, and reduce data loss due to patient loss to follow-up. If there is data loss due to patient loss to follow-up, it should be excluded from data analysis and appropriately documented.

# **8 Adverse Events and Unexpected Events**

## **8.1 Adverse event**

Adverse events (AE) refer to all adverse medical events that occur in subjects after receiving the investigational drug. They can manifest as symptoms, signs, diseases, or laboratory abnormalities, but are not necessarily causally related to the investigational drug.

The grading of adverse events is as follows:

Grade 1: Mild; asymptomatic or mild symptoms; only clinical or diagnostic manifestations; no intervention required;

Grade 2: Moderate; requires minimal, partial, or non-invasive intervention; restricts appropriate age daily activities;

Grade 3: Severe or significant medical events that require drug treatment, but do not immediately threaten life; hospitalization or prolonged hospitalization; disability; restricts activities of daily living (ADLs);

Grade 4: Life-threatening consequences; requires urgent intervention;

Grade 5: Death related to AE.

## **8.2 Serious Adverse Event**

Serious adverse events (SAEs) are adverse events that meet at least one of the following criteria:

1. Results in death, excluding death related to progression of the disease under investigation.
2. Puts the subject's life at risk ("life-threatening" as defined by the fact that the event places the subject at risk of death at the time of the AE, not necessarily that death is a possible outcome if the condition worsens).
3. Results in permanent or significant disability/incapacity.
4. Other medically important events: defined as an event that endangers the subject or requires medical intervention to prevent any of the above outcomes from happening.

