### **4.4 Recruitment and Retention Strategies**

At the outpatient and ward departments of Traditional Chinese Medicine and Rehabilitation of Sun Yat-sen Memorial Hospital, eligible MCI patients with the type of kidney deficiency and phlegm stasis were identified according to the inclusion criteria. After fully communicating trial-related information with the patients, they

[figure not shown]
were informed of the possible adverse reactions and risks, and asked to sign an informed consent form voluntarily and informed about the trial plan.

Retention strategies: (1) Researchers should maintain one-on-one communication with patients as much as possible. (2) Clear trial-related information should be provided to patients during the first communication, along with a process calendar, and patients should be informed of the next appointment time and reminded through phone calls. (3) Researchers can communicate the current progress with patients at appropriate times to help them fully recognize their contribution to the research. (4) Sufficient work should be done to obtain informed consent during the screening phase and to answer any questions patients may have.

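### Under section 8.2, hospital admission or a prolonged stay does not by itself make an adverse event serious, although section 8.1 lists it beside disability in Grade 3

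*Protocol*

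**What the plan says.** Protocol section 8.2 opens with the rule: "Serious adverse events (SAEs) are adverse events that meet at least one of the following criteria". Four numbered criteria follow:

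1. "Results in death, excluding death related to progression of the disease under investigation".
2. A threat to life, explained as meaning that "the event places the subject at risk of death at the time of the AE".
3. "Results in permanent or significant disability/incapacity".
4. A catch-all for events of medical importance, which the section spells out this way: "defined as an event that endangers the subject or requires medical intervention to prevent any of the above outcomes from happening".

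Section 8.1 grades adverse events from 1 to 5. Grade 3 covers severe or significant events that need drug treatment without being immediately life-threatening. Its markers include "hospitalization or prolonged hospitalization; disability", followed by restriction in activities of daily living.

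Section 4.4 gives the recruitment setting: "At the outpatient and ward departments of Traditional Chinese Medicine and Rehabilitation". Some participants may therefore already be in hospital when they join.

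No other section of the protocol gives an SAE definition or a rule on hospitalisation. The numbering in 8.2 runs from 1 to 4 without a gap or redaction mark, so nothing suggests that a criterion was lost.

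**The concern.** The protocol treats admission and disability as companions when it grades severity, then keeps only one of them when it defines seriousness. Someone applying 8.2 as written would not classify an event as serious because the patient was admitted or stayed longer. That step would need a separate judgement under the fourth criterion.

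This matters because safety is a declared aim (section 1 and the end of section 2) and has its own analysis set (section 5.4.2). Participants are aged 55 to 85 (section 4.1), may have hypertension or diabetes (sections 4.3 and 5.1), come partly from wards, and are treated for 12 weeks (section 6.1). New admissions and prolonged stays are both possible in such a group. One arm adds herbal granules to the control drug and no masking is described. A classification that rests on judgement could therefore be applied differently in the two arms, and any statement about SAEs would depend on it.

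**Working it through.** The protocol has no figure to reproduce here. The check sets the two lists side by side.

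| Outcome | Section 8.1 (grade) | Section 8.2 (SAE criterion) |
|---|---|---|
| Death | Grade 5 | Criterion 1, with an exclusion for progression of the disease under study |
| Threat to life | Grade 4 | Criterion 2 |
| Disability | Grade 3 | Criterion 3 |
| Admission or prolonged stay | Grade 3 | None |
| Need for drug treatment | Grade 3 | None as such |
| Restricted daily activities | Grade 3 | None as such |

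Hospitalisation is named in 1 of 5 grades and in 0 of 4 SAE criteria.

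Now take an event whose only notable feature is that the patient was admitted, or kept in longer, and run it through 8.2:

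- Criterion 1: the patient did not die, so it is not met.
- Criterion 2: Grade 3 describes events that do not immediately threaten life, so an event correctly placed there would not normally meet it.
- Criterion 3: there is no lasting or significant disability, so it is not met.
- Criterion 4, second limb: this covers intervention to prevent the outcomes listed above it. Those are death, threat to life and disability. Hospitalisation is not among them, so admission as such does not trigger it.
- Criterion 4, first limb: this covers an event that endangers the subject. The term is not defined, so the answer depends on the assessor.

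The event is thus a Grade 3 adverse event, and an SAE only by judgement.

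The Grade 3 total does not fill the gap. It pools drug treatment, admission, disability and restricted activities, so it does not show how many patients were admitted or stayed longer.

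**Illustration of scale, on an assumption.** The documents give no admission rate. Suppose 1% to 5% of the 64 patients (section 5.4.1), independently of one another, were admitted or had a stay prolonged during treatment:

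- Expected number: 64 × 0.01 = 0.64 to 64 × 0.05 = 3.2.
- Chance of none: 0.99^64 = 0.53 at 1%, and 0.95^64 = 0.04 at 5%.
- Chance of at least one: 0.47 to 0.96.

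These figures count all admissions. The number left out of the SAE count would be at most this, because some admissions would qualify under criteria 1 to 4.

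**The case against.** Four points can be made on the other side.

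*Severity and seriousness are different axes.* Section 8.1 grades the one and 8.2 defines the other, and nothing says that a Grade 3 feature makes an event serious. Drug treatment and restricted activities are also in Grade 3 and are not carried over, so the lists were not built to match item by item. This stands: there is no formal contradiction. What remains is a definition that omits an outcome the protocol itself ranks with disability.

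*The fourth criterion is broad.* Many unplanned admissions in patients of this age could be judged to endanger them. This also stands, in part. A reader might infer that patients admitted to hospital would never be counted as SAEs. The text does not support that, because an admission counts if the event is fatal, life-threatening, disabling or judged endangering. What is lost is automatic classification when admission is the only feature.

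*Nothing goes unrecorded.* Admission is a Grade 3 marker, and the calendar in section 5.2 has adverse events and the case report form completed throughout. This stands: the events would be in the data and could be reclassified later. It limits the harm to the SAE label and count.

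*The label carries little weight in this document.* Sections 8.1 and 8.2 attach no reporting deadline or decision rule to an SAE, section 3.4 lists laboratory tests, electrocardiogram and adverse reactions rather than an SAE count, and section 3.1 states the main purpose as efficacy. This is fair and keeps the point modest. But a protocol that defines SAEs and sets up a safety analysis set invites a statement about them, and that statement should not depend on an undefined term.

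**Conclusion.** The point holds in a limited form. Under 8.2, hospitalisation or prolonged hospitalisation alone does not make an event serious, although 8.1 names it beside disability. Events with no other qualifying feature would enter the record as Grade 3 and become SAEs only by judgement, without described masking. The SAE count could therefore be too low.

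The size is unknown. A reader might take the illustrative range to mean that the true SAE count is one to three while the report shows zero. The documents do not support that: the rate is assumed, at its lower end no admission at all is more likely than not (0.53), and some admissions would be serious under the existing criteria. Nor do the ages, comorbidities and ward recruitment show that admission is the likeliest serious event; they show only that it is possible.

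The efficacy analysis and power are unaffected. This is a badly fixed definition, worth correcting, and not a threat to the validity of the trial.

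**What to change.** Reconcile 8.2 with 8.1 by adding one criterion to the SAE list: the event results in hospitalisation or prolongs existing hospitalisation. Place it before the catch-all, so that the reference there to the outcomes above also takes it in.

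The protocol describes the study as retrospective, so data may already have been collected. In that case, review the recorded adverse events for admission or prolonged stay, and classify and tabulate them by the same rule in both arms.

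The cost is one line of text, slightly more SAE paperwork and possibly a less favourable SAE count. Adverse events are already collected throughout, so no new visit or assessment is required.

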## **9 Data collection and management**

All patient clinical testing reports in this project strictly adhere to the legally prescribed national unit of measurement. The patient testing and follow-up records must be complete, including the date, recorded items, results, and normal value ranges, among other information, and must be signed by relevant personnel. Clinical case data and follow-up data are recorded and collected by trained and professional data

collection and management personnel, and reviewed and confirmed for accuracy by the team leader before being entered into the database.

## **10 Ethical Requirements**

This study follows the "Guidelines for Good Clinical Practice" and "Management Measures for Clinical Trials Initiated by Researchers in Medical Institutions" (trial) regulations, as well as the Helsinki Declaration. Before the trial can begin, the study protocol must be approved by the hospital ethics committee. If revisions to the protocol are necessary during the study, the updated version must be resubmitted to the ethics committee for review, and the researcher can proceed only with their approval.

Every patient who is enrolled in the study must sign an informed consent form. Copies of the informed consent form and contact information for the researcher and ethics committee must be provided to patients upon request. This study will collect clinical data and personal information for scientific research purposes, which may involve patient privacy. All participants and data analysts involved in the study have signed confidentiality agreements and will not disclose any patient information or disease-related information to any unrelated individuals or organizations. The collected patient data will be managed uniformly to prevent personal privacy from being leaked.

